**How to clean your inhaler**

- Clean your inhaler once a week.
- Wipe the mouthpiece inside and outside to remove any powder with a clean, dry lint-free cloth.
- Do not wash your inhaler with water. Keep it dry.
- Do not take the inhaler apart.

2.7.3 Other safety data	18
2.8 Pharmacokinetic endpoints.....	20
2.9 PD and PK/PD analyses	20
2.10 Patient-reported outcomes	20
2.11 Biomarkers.....	20
2.12 [REDACTED].....	20
2.13 Interim analysis.....	21

3	Sample size calculation	21
4	Change to protocol specified analyses	22
5	Appendix	22
5.1	Imputation rules	22
5.2	AEs coding/grading	22
5.3	Laboratory parameters derivations	22
	Direction of interest and definition of clinically notable values	22
5.4	Statistical models	24
5.4.1	Primary analysis	24
5.4.2	Key secondary analysis	24
5.5	Rule of exclusion criteria of analysis sets.....	24
6	Reference	25

List of abbreviations

AE	Adverse event
ATC	Anatomical Therapeutic Classification
AUC	Area Under the Curve
bid	bis in diem/twice a day
CSR	Clinical Study report
CTC	Common Toxicity Criteria
CTCAE	Common Terminology Criteria for Adverse Events
DMC	Data Monitoring Committee
FAS	Full Analysis Set
eCRF	Electronic Case Report Form
IVR	Interactive Voice Response
IWR	Interactive Web Response
MedDRA	Medical Dictionary for Drug Regulatory Affairs
NCI	National Cancer Institute
o.d.	Once Daily
OS	Overall Survival
PFS	Progression-Free Survival
PK	Pharmacokinetics
PPS	Per-Protocol Set
PRO	Patient-reported Outcomes
qd	Qua'que di'e / once a day
QoL	Quality of Life
RAP	Report and Analysis Process
RECIST	Response Evaluation Criteria in Solid Tumors
SAP	Statistical Analysis Plan
SOC	System Organ Class
TFLs	Tables, Figures, Listings
WHO	World Health Organization

1 Introduction

This document contains details of the statistical methods that will be used in the phase III clinical trial CQVM149B1305. This study is designed to provide long term safety data of QMF149 in Japanese patients with asthma for the registration of QMF149 in Japan.

Data will be analyzed according to Section 9 of the study protocol.

Important information and details are given in the following sections.

1.1 Study design

This study uses a 52-week treatment, multicenter, open-label, single-arm design in Japanese patients with asthma. One interim analysis is planned after the last patient completed the assessments at Week 26 (Visit 107).

This study is designed to obtain safety data of QMF149 in 59 Japanese asthma patients. Details of sample size are described in [Section 3](#) in this document.

No randomization is planned in this study.

The primary objective of this study is to assess the safety/tolerability of 52 weeks of treatment with QMF149 (150/320 µg, once daily), particularly with regard to treatment emergent adverse event reporting in Japanese patients with inadequately controlled asthma.

The primary variable is the number and percentage of patients who reported treatment emergent adverse events during the 52 week study period.

An interim analysis for 6-month data will be performed for the initial New Drug Application submission in Japan. This analysis will be performed after all patients have been enrolled and completed Visit 107 (Week 26) or discontinued the study. Details of the interim analysis are described in [Section 2.13](#) in this document.

1.2 Study objectives and endpoints

Objective(s)	Endpoint(s)
Primary Objective(s) 
To assess the safety/tolerability of 52 weeks of treatment with QMF149 (150/320 µg, once daily) in Japanese patients with inadequately controlled asthma.	Endpoint(s) for primary objective(s) 
The incidence and severity of treatment emergent adverse events (AEs) over 52 weeks of treatment
Secondary Objective(s) 
To assess the safety of QMF149 over 52 weeks of treatmentTo assess the efficacy of QMF149 in terms of lung-function in Japanese patients with inadequately controlled asthma.	Endpoint(s) for secondary objective(s) 
ECG, vital sign (blood pressure, pulse rate), laboratory parameters (hematology, clinical chemistry and urinalysis), plasma cortisol over 52 weeks of treatmentChange from baseline of pre-dose FEV₁ measured after 26 and 52 weeks treatmentChange from baseline of morning and evening PEF during 52 weeks treatment

Objective(s)	Endpoint(s)

To assess the efficacy of QMF149 in terms of asthma control.	
Change from baseline of ACQ-7 after 26 and 52 weeks treatmentResponder rate of patients achieving the minimal important difference (MID) of ACQ-7 ≥ 0.5 after 26 and 52 weeks treatment

To assess the efficacy of QMF149 in terms of rescue medication use	
Change from baseline of rescue medication use during 52 weeks treatment

2 Statistical methods

2.1 Data analysis general information

All data analysis will be performed by Novartis according to the data analysis section 9 of the study protocol using the most actual version of SAS at the time of database lock.

General descriptive statistical rules to summarize quantitative or qualitative parameter are: continuous variables will be summarized using descriptive statistics (number of non-missing data, mean, median, standard deviation, first and third quartiles, minimum, and maximum) and categorical variables will be summarized in terms of the number and percentage of patients in each category including a category for missing data if any.

The analysis will be conducted on all subject data at the time the trial ends.

Any data analysis carried out independently by the investigator should be submitted to Novartis before publication or presentation.

2.1.1 General definitions

Study day is defined as the number of days since the date of first dose of study medication. The date of first dose of study medication was defined as Day 1 and the day before the first dose of study medication was defined as Day -1.

Therefore, for a particular date, study day will be calculated as follows:

- for dates on or after the first date of study medication,
Study day = Assessment date – Date of first dose of study medication + 1;
- for dates prior to the first date of study medication,
Study day = Assessment date – Date of first dose of study medication.

In general, baseline is defined as the last measurement before the first dose of study drug at Day 1. Refer to the baseline definitions for each analysis described in the later sections.

When change from baseline is of interest the following formula will be used for each scheduled visit and time-point where baseline and post-baseline values are both available:

Change from baseline = post-baseline value – baseline value

Data from unplanned or unscheduled visits or the early treatment/study discontinuation visits will be listed. For patients who do not complete the study, the treatment discontinuation visit will be an unscheduled visit. Clinical laboratory measurements, vital signs and ECG data from unplanned or unscheduled visits will only be included in the summaries of the notable values and extreme values. All efficacy data (including spirometry data) from these visits will not be used for missing data imputation unless specified otherwise. Laboratory, vital signs, and ECG values that have complete data and time values will be slotted into pre- or post-dose assessment based on the actual date/time. For values with missing date/time, their respective scheduled visit date and time will be used. This rule will be applied to data from scheduled visits only. If a measurement scheduled as pre-dose is actually performed post-dose, or vice versa, the data will not be used for by time point assessments but will be included in the summaries of the notable values and extreme values.

2.2 Analysis sets

The Safety Set will consist of all patients who received at least one dose of study medication during this study. The Safety Set will be used in the analysis of all safety variables.

Full Analysis Set (FAS) will consist of all patients who entered in the treatment epoch of this study and received at least one dose of study medication during this study. The efficacy analysis will be based on FAS.

Note that the Safety Set and FAS are the same except that the Safety Set allows the inclusion of patients who are not intended to enter in the treatment epoch of this study but received study drug in error.

2.2.1 Subgroup of interest

- Age (18 - < 65years, ≥ 65years)
- Sex (male, female)
- Pre-bronchodilator FEV₁ in % of predicted FEV₁ at screening Visit 2 (< 50%, 50% - < 60%, 60% - ≤ 85%, > 85%)

Refer to the [Section 2.5.4](#) in this document.

2.3 Patient disposition, demographics and other baseline characteristics

Demographics and baseline characteristics including age, sex, race, ethnicity, height, weight, body mass index (BMI), relevant medical history, screening spirometry parameters: (FEV₁, FVC, and FEV₁/FVC), FEV₁ reversibility, percentage of predicted FEV₁, baseline PEF, duration of asthma, history of asthma exacerbations, smoking history, prior concurrent medications (asthma-related and non-asthma-related), vital signs (systolic and diastolic blood

pressure, pulse rate), QTc using Fridericia's correction and baseline ACQ-7, will be summarized on safety set.

Baseline is defined as the last measurement before first dose of study drug. Missing baseline will not be imputed, unless otherwise specified.

In addition, the following categorizations of continuous variables will be done:

- Age into 18 - 39 years, 40 - 64 years, and ≥ 65 years;
- BMI into $< 25.0 \text{ kg/m}^2$, $25.0 - 30.0 \text{ kg/m}^2$, and $> 30.0 \text{ kg/m}^2$;
- Duration of asthma into < 1 year, 1 - 5 years, $> 5 - 10$ years, $> 10 - 15$ years, $> 15 - 20$ years, and > 20 years;
- Number of asthma exacerbations in the 12 months prior to the start of the study that required medical care into 1, 2, 3, ≥ 4 ;
- pre-bronchodilator FEV₁ into $< 50\%$, $50\% - < 60\%$, $60\% - \leq 85\%$, $> 85\%$ of predicted FEV₁;
- ACQ-7 into < 1.5 , $1.5 - < 2$, $2 - < 2.5$, ≥ 2.5 .

Medical history will be coded with the Medical Dictionary for Regulatory Activities terminology (MedDRA) using the most actual version at the time of database lock. History/conditions will be summarized for the Safety Set by primary system organ class and preferred term. Verbatim recorded history/conditions will be listed together with the coded terms, date of diagnosis/surgery and whether the problem was ongoing at start of the study.

In addition, medical histories/current medical conditions will be summarized by their status at baseline (current medical conditions, past medical conditions) and primary system organ class. Current medical conditions are defined as those which were reported as "Ongoing" at baseline.

2.3.1 Patient disposition

For each study epoch (i.e., screening, treatment phase, post treatment follow-up), the overall number of patients who entered, completed, and discontinued that phase will be summarized including the reasons for discontinuation.

The number of patients included in each analysis set will be tabulated, as well as the reasons for exclusions from analysis sets. Patient exclusion from analysis sets will be listed for all patients with reasons for exclusion (including both CSR-reportable and non CSR-reportable protocol deviations).

The number of patients with protocol deviations will be tabulated by category (e.g., selection criteria not met, prohibited concomitant medication, key procedures not performed as per protocol) and deviation for the Safety Set. Protocol deviations will be listed with date and study day of occurrence, deviation and analysis populations from which patients are excluded.

2.4 Treatments (study treatment, rescue medication, concomitant therapies, compliance)

2.4.1 Study treatment / compliance

Study drug administration and concomitant medication data will be listed and summarized using the Safety Set.

The duration of exposure and the number of patients who completed the study medication and who discontinued from the study medication will be summarized. Duration of exposure to study treatment will be calculated as the number of days starting from the first dose date up to and inclusive the last dose date. The duration of exposure will be summarized for the Safety Set as a continuous variable with the standard descriptive statistics. In addition, the duration of exposure will be summarized with total patient years and the number (%) of patients who were exposed to study drug for each 1 - 29 days, 30 - 86 days, 87 - 183 days, 184 - 254 days, 255 - 365 days, and > 365 days. The number of patients who completed the 52-week study treatment and who discontinued prematurely will be shown including the reasons for discontinuation of study treatment.

Treatment compliance with study medication over the study period will be summarized. Compliance will be calculated by counting the days where study drug was administered "As per protocol" according to the records on the Dosage Administration Record (DAR) Summary eCRF. The percentage of days divided by the days of exposure will be analyzed. Compliance will be categorized into < 80% and 80% - 100% and summarized for the Safety Set.

2.4.2 Prior, concomitant and post therapies

Medications started and stopped prior to study drug, and taken concomitantly will be summarized for the Safety Set. Prior medications are defined as drugs taken and stopped prior to first dose of study medication. Any medication given at least once between the day of first dose of study medication and last day of study visit will be a concomitant medication, including those which were started pre-baseline and continued into the treatment period.

Concomitant therapies will be recorded, listed and summarized separately for asthma related medications/non-drug therapies and other medications.

Separate tables will be provided for medications which were started and stopped prior to the first dose of study drug and medications which were taken concomitantly to the study drug (regardless of whether continued or started after the first dose of study drug).

Asthma medications will be summarized by the route of administration, the recorded pre-specified drug subcategories (including types of combination) and the coded preferred terms. The summary will be repeated by showing ingredients instead of preferred terms.

Non-asthma medications will be summarized by route of administration and the coded preferred terms.

Surgical and medical procedures (non-drug therapies) will be coded using MedDRA and presentations will be done by MedDRA primary system organ class and preferred term, separately for prior procedures and those after start of study drug.

Short acting beta2 agonist (SABA) rescue medication usage (number of puffs) during the screening epoch will be summarized.

Patients taking prohibited concomitant medications will be noted in the summary of protocol deviations.

2.5 Analysis of the primary objective

The primary objective of this study is to assess the safety/tolerability of 52 weeks of treatment with QMF149 (150/320 µg, once daily), particularly with regard to treatment emergent adverse event reporting in Japanese patients with inadequately controlled asthma.

2.5.1 Primary endpoint

The primary variable is the number and percentage of patients who reported treatment emergent adverse events during the 52 week study period for the Safety set.

All treatment emergent adverse events including asthma exacerbations will be summarized and listed. Adverse events starting on or after the time of the first inhalation of study drug but not later than 7 days (30 days in the case of a SAE) after the last administration will be classified as a treatment emergent adverse event. Any adverse events that started during the study before the time of the first inhalation of study drug will be classified as a prior adverse event.

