## 2 Study objectives and endpoints

### 2.1 Objectives and related endpoints

**Table 2-1 Objectives and related endpoints**

Objective(s)	Endpoint(s)
Primary Objective(s)	Endpoint(s) for primary objective(s)

 
To assess the safety/tolerability of 52 weeks of treatment with QMF149 (150/320 µg, once daily) in Japanese patients with inadequately controlled asthma.
 
	
 
The incidence and severity of treatment emergent adverse events (AEs) over 52 weeks of treatment
 

Secondary Objective(s)	Endpoint(s) for secondary objective(s)

 
To assess the safety of QMF149 over 52 weeks of treatment
 
To assess the efficacy of QMF149 in terms of lung-function in Japanese patients with inadequately controlled asthma.
 
To assess the efficacy of QMF149 in terms of asthma control.
 
	
 
ECG, vital sign (blood pressure, pulse rate), laboratory parameters (hematology, clinical chemistry and urinalysis), plasma cortisol over 52 weeks of treatment
 
Change from baseline of pre-dose FEV1 measured after 26 and 52 weeks treatment
 
Change from baseline of morning and evening PEF during 52 weeks treatment
 
Change from baseline of ACQ-7 after 26 and 52 weeks treatment
 
Responder rate of patients achieving the minimal important difference (MID) of ACQ-7 ≥ 0.5 after 26 and 52 weeks treatment
 

1) To assess the efficacy of QMF149 in terms of rescue medication use	1. Change from baseline of rescue medication use during 52 weeks treatment

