## 7 Safety monitoring

### 7.1 Adverse events

An adverse event (AE) is any untoward medical occurrence (e.g., any unfavorable and unintended sign [including abnormal laboratory findings], symptom or disease) in a subject or clinical investigation subject *after providing written informed consent* for participation in the study until the end of study visit. Therefore, an AE may or may not be temporally or causally associated with the use of a medicinal (investigational) product.

In addition, all reports of intentional misuse and abuse of the product are also considered an adverse event irrespective if a clinical event has occurred.

The occurrence of adverse events must be sought by non-directive questioning of the patient at each visit during the study. Adverse events also may be detected when they are volunteered by the patient during or between visits or through physical examination findings, laboratory test findings, or other assessments.

Abnormal laboratory values or test results constitute adverse events only if they fulfill at least one of the following criteria:

- they induce clinical signs or symptoms,
- they are considered clinically significant,
- they require therapy.

Clinically significant abnormal laboratory values or test results must be identified through a review of values outside of normal ranges/clinically notable ranges, significant changes from baseline or the previous visit, or values which are considered to be non-typical in patient with underlying disease. Investigators have the responsibility for managing the safety of individual patient and identifying adverse events. Alert ranges for laboratory and other test abnormalities are included in [Appendix 1](#).

Adverse events must be recorded in the Adverse Events CRF under the signs, symptoms or diagnosis associated with them, accompanied by the following information:

- the severity grade
- mild: usually transient in nature and generally not interfering with normal activities
- moderate: sufficiently discomforting to interfere with normal activities
- severe: prevents normal activities
- its relationship to the study treatment
- Yes
- No
- its duration (start and end dates) or if the event is ongoing an outcome of not recovered/not resolved must be reported.
- whether it constitutes a serious adverse event (SAE - See [Section 7.2](#) for definition of SAE) and which seriousness criteria have been met.
- action taken regarding investigational treatment

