All adverse events must be treated appropriately. Treatment may include one or more of the following:

- no action taken (e.g. further observation only)
- investigational treatment dosage increased/reduced
- investigational treatment interrupted/withdrawn
- concomitant medication given
- non-drug therapy given
- patient hospitalized/patient's hospitalization prolonged (see [Section 7.2](#) for definition of SAE)
- its outcome (not recovered/not resolved; recovered/resolved; recovering/resolving, recovered/resolved with sequelae; fatal; or unknown)

Once an adverse event is detected, it must be followed until its resolution or until it is judged to be permanent, and assessment must be made at each visit (or more frequently, if necessary) of any changes in severity, the suspected relationship to the study drug, the interventions required to treat it, and the outcome.

Information about common side effects already known about the investigational drug can be found in the Investigator Brochure (IB). This information will be included in the patient informed consent and should be discussed with the patient during the study as needed. Any new information regarding the safety profile of the medicinal product that is identified between IB updates will be communicated as appropriate, for example, via an Investigator Notification or an Aggregate Safety Finding. New information might require an update to the informed consent and has then to be discussed with the patient.

The investigator must also instruct each patient to report any new adverse event (beyond the protocol observation period) that the patient, or the patient's personal physician, believes might reasonably be related to study treatment. This information must be recorded in the investigator's source documents; however, if the AE meets the criteria of an SAE, it must be reported to Novartis.

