2.5.2 Statistical hypothesis, model, and method of analysis

Adverse events will be summarized with descriptive statistics for the Safety Set.

The number and percentage of patients who reported treatment emergent adverse events will be summarized by primary system organ class, preferred term for

- All adverse events
- All adverse events by time at onset (≤ 12 weeks, $> 12 - \leq 26$ weeks, > 26 weeks)
- Serious adverse events
- Adverse events by maximum severity
- Adverse events suspected to be related to study drug
- Adverse events leading to permanent study drug discontinuation
- Adverse events of special interest

All adverse events including asthma exacerbations, coded with MedDRA using the most actual version at the time of database lock, will be listed.

Unless otherwise specified, primary system organ classes will be sorted alphabetically and, within each primary system organ class, the preferred terms will be sorted in descending order of frequency. If a patient reported more than one adverse event with the same preferred term, the adverse event will be counted only once. If a patient reported more than one adverse event within the same primary system organ class, the patient will be counted only once at the system organ class level.

In addition, the most frequent adverse events will be presented by preferred term in descending order of frequency.

For AEs by maximum severity, missing severity will be assumed to be severe in the summary table.

A composite endpoint of serious asthma outcomes is defined as a) asthma-related hospitalization, b) asthma-related intubation, or c) asthma-related death. All serious asthma outcomes and deaths occurring from the treatment epoch until the 30 days after permanent discontinuation of study drug will be adjudicated by an independent external committee to determine their asthma relatedness.

The composite endpoint as well as each single component of it will be analyzed for the number of patients with the event, the time to event and the annual rate of events.

The Compound Case Retrieval Strategy (CRS) will be used to determine the MedDRA search criteria to be used to identify events of special interest. The most recent list of adverse events of special interest at the time of database lock will be used.

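### Treatment-emergent status rests on AE start time alone, so a screening-onset AE that worsens on QMF149 can fall outside the primary safety tables

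*SAP*

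**What the plan says.** **Classification.** SAP 2.5.1 and Protocol 9.4.1 use the same rule. An AE is treatment-emergent if it starts from first inhalation up to 7 days after the last dose (30 days for an SAE). An event that "started during the study before the time of the first inhalation of study drug will be classified as a prior adverse event". Neither section mentions worsening, and SAP 5.2 only refers back to SAP 2.5.

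**Collection.** Protocol 7.1 counts AEs that arise "after providing written informed consent", so screening events are recorded. For each event the CRF takes "its duration (start and end dates"), a severity grade, relationship, seriousness and action taken. Once detected, an event "must be followed until its resolution or until it is judged to be permanent". Sites also check, visit by visit, whether its severity has changed.

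**Serious events.** The SAE definition in Protocol 7.2.1 covers worsening of a pre-existing condition as well as a new appearance. Protocol 7.2.2 has progression reported as follow-up to the original event.

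**Use.** Table 2-1 of the protocol gives the primary endpoint as "The incidence and severity of treatment emergent adverse events (AEs") over 52 weeks. SAP 2.5.2 restricts its tables to treatment-emergent events, including "Adverse events by maximum severity" and "Adverse events leading to permanent study drug discontinuation".

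**The concern.** Take a patient with a mild AE that begins in screening and becomes severe, or serious, some weeks into QMF149. If the record keeps its original start date, the rule makes the whole event prior. It is then missing from every treatment-emergent table in SAP 2.5.2: preferred term, maximum severity, SAE, relatedness and discontinuation. It appears only in the listings.

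Severity is half of the primary endpoint, so the maximum-severity table is part of the primary result. In a single-arm safety study of about 66 patients, a single severe or serious event carries weight. Two tables could also disagree. A patient who stops because such an event worsened is counted among the reasons for discontinuation (SAP 2.4.1) but not among AEs leading to discontinuation (SAP 2.5.2).

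The SAP treats measured safety data differently. For laboratory values, QTc and vital signs it counts abnormalities that are new or worse than baseline (SAP 2.7.2, 2.7.3.1, 2.7.3.2). AEs have no counterpart.

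**Working it through.** **1. What the text does with a worsening event**

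| Question | Where | Answer |
|---|---|---|
| What decides treatment-emergent status? | SAP 2.5.1, Protocol 9.4.1 | Start time only |
| Are screening AEs recorded? | Protocol 7.1, Table 6-1 | Yes, from consent |
| Does a severity change open a new record? | Protocol 7.1 | Not stated; one followed event is described |
| How is SAE progression reported? | Protocol 7.2.2 | As follow-up to the original event |
| Can worsening itself be an SAE? | Protocol 7.2.1 | Yes |

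The general text leans towards one record with its first start date. Protocol 7.2.1 points the other way for serious worsening. No passage settles the AE start date.

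**2. The denominator.** The plan's figures reproduce. The target is 100 − 41 = 59 completers; 59/0.90 = 65.6, so 66 treated; 66/0.75 = 88 screened (Protocol 9.8, SAP 3).

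**3. Weight of one patient.** 1/66 = 1.5 percentage points. A patient leaves the headline percentage only if the worsened screening AE is their sole on-treatment event.

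**4. Expected number.** The documents give neither an AE rate nor a worsening rate, so these are assumptions: r = 1 to 3 AEs per patient-year, and a share w = 2% to 10% of screening-onset AEs worsening on drug. Screening lasts s = 2 to 4 weeks (Figure 3-1 notes).

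- Worsened AEs = 66 × s/52 × r × w
- Chance of no other AE in about one year, if AEs follow a Poisson process = exp(−r)
- Patients lost from the headline = worsened AEs × exp(−r)

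| s (weeks) | r | w | Screening-onset AEs | Worsened AEs | exp(−r) | Patients lost | Points of 66 |
|---|---|---|---|---|---|---|---|
| 2 | 1 | 2% | 2.5 | 0.05 | 0.37 | 0.02 | 0.03 |
| 2 | 3 | 2% | 7.6 | 0.15 | 0.05 | 0.008 | 0.01 |
| 4 | 3 | 10% | 15.2 | 1.52 | 0.05 | 0.08 | 0.11 |
| 4 | 1 | 10% | 5.1 | 0.51 | 0.37 | 0.19 | 0.28 |

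Because r × exp(−r) is largest at r = 1, no other AE rate gives more than the last row for the same s and w.

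**5. Events missing from the detailed tables.** Here the relevant column is worsened AEs: 0.05 to 1.5 events on the same assumptions.

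**6. These figures are upper guides.** AEs that resolve before Day 1 cannot worsen on drug. Respiratory infection, exacerbation and significant candidiasis in screening bar entry, as do significant ECG or laboratory abnormalities at Visit 2 (Protocol 4.2). Significant asthma worsening in screening does too (Protocol 6.4.4).

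**The case against.** The strongest objection is that the harm depends on a document we do not have. CRF-completion guidance often sits outside a protocol and SAP. If it tells sites to open a new record when an event worsens, the start-time rule already captures the change and nothing is lost. Protocol 7.2.1 gives some support for serious worsening. This stands as a condition on the point, but it does not remove the gap: the rule as written has no worsening exception, and Protocol 7.1 and 7.2.2 do not direct sites to a new record.

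A second objection is that this is a preference. Protocol and SAP agree word for word, the analysis is descriptive with no test to bias, and the laboratory and ECG rules concern numeric values against a baseline. That is fair: a reader might infer an internal contradiction, and there is none. The comparison shows only that the SAP recognises worsening elsewhere.

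Third, the information is not wholly lost. All AEs are listed. Reasons for discontinuation, deaths and adjudicated serious asthma outcomes are summarised with no condition on AE onset (SAP 2.3.1, 2.4.1, 2.5.2, 2.7.1.1). This stands, and it confines the loss mainly to the severity, seriousness, relatedness and preferred-term detail of other AEs.

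A reader might also set one AE-led stop against the 7 planned dropouts (66 − 59) and say that 1/7 = 14% goes missing. Those 7 are dropouts from any cause. The documents give no AE-led count, so the fraction has no proper denominator.

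**Conclusion.** The point holds as a gap in a stated rule, and it is worth closing. As written, on-drug worsening of a screening-onset AE is classed as prior unless an unseen CRF convention creates a new record.

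A reader might infer that the headline AE percentage is materially understated, for example by 1.52/66 = 2.3 points in the high case. The documents do not support that. Such a figure treats every worsened event as a patient lost, whereas a patient with any other treatment-emergent AE is already counted. Allowing for this, the expected shift is about 0.01 to 0.3 points. That rests on the assumed rates and the Poisson model, before the entry bars are applied.

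What is at stake is the detail of perhaps zero to two events. Each could be severe or serious, and each would be absent from the tables that report the severity half of the primary endpoint. The sample size is unaffected.

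**What to change.** In Protocol 9.4.1 and SAP 2.5.1, extend the definition. An AE with onset before first inhalation is also treatment-emergent if it increases in severity or becomes serious after first inhalation, within the same 7-day window (30 days for an SAE). Date it at the change for the onset-time bands in SAP 2.5.2, and use the severity reached on treatment in the maximum-severity table.

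In the CRF guidance, have the AE record capture the date of the change. A linked record or an added date field would serve. Either must be reconciled with Protocol 7.2.2, so that an event that becomes serious is not handled one way on the AE page and another on the SAE form. No separate criterion is needed for discontinuation without worsening; a stop caused by a worsened AE enters the discontinuation table through the new clause.

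If the guidance already opens a new record on worsening, stating that in both documents is enough.

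**Cost.** A short written amendment (Protocol 11.1), a matching SAP edit and a line of CRF guidance, with no added visits or patients. Reported counts become slightly less favourable. Because Protocol 9.8 relies on about 41 patients from CQVM149B2301 and B2302 to reach 100, the definition should be checked against theirs before data are combined; those definitions are not in these documents.
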